## 6.2 PREPARATION/HANDLING/STORAGE/ACCOUNTABILITY

### 6.2.1 ACQUISITION AND ACCOUNTABILITY

We will use a vitamin D3 supplement in this study because vitamin D2 is only approximately 30% as effective as vitamin D3 in maintaining serum 25(OH)D levels.(79) Bio-Tech Pharmacal, Inc. will package and supply all vitamin D3 products for use in this study. The products are licensed, approved drugs. Specific details of this product will be provided to study sites in the MOP. Capsule ingredients include vitamin D3 power (containing cholecalciferol 0.25% and polyethylene glycol 99.5%), microcrystalline cellulose, and gelatin capsule. Ingredients are free from microbiological content and meet USP specification.

### 6.2.2 FORMULATION, APPEARANCE, PACKAGING, AND LABELING

All vitamin D3 doses will be packed in blister packs or individually labeled bottles. The loading doses will be packaged separately from the daily doses; loading doses will be given directly to participants to take during visit 2. Participants will take home the labeled bottles/packs for their daily (i.e., all but visit 2) doses. Vitamin D supplements will be provided in the form of a size 2 capsule, either gelatin or hypromellose (vegetable). The capsules used for all doses in Part 1 were gelatin. The D3 (4000 IU) capsules for Part 2 are vegetable capsules. Size 2 capsules are approximately 18 mm in length (0.71 inches) with an outside diameter of 6.3 mm (0.24 inches).

### 6.2.3 PRODUCT STORAGE AND STABILITY

This product is to be stored at room temperature approximately 20°C), away from moisture and light. All temperature excursions at sites must be appropriately recorded and reported to the study sponsor for further evaluation and follow-up.

#### 6.2.4 PREPARATION

The product will be kept ready for administration in a sealed bottle or blister packs. No additional preparation is required. However, either the pharmacist or designee will do a pill count prior to giving the bottle to the participant. For details on the pill count, refer to the pharmacy manual.

### 6.3 MEASURES TO MINIMIZE BIAS: RANDOMIZATION AND BLINDING

#### Randomization

Randomization of participants will be done online using the randomization module of the DCOC electronic data capture system. For the first part of the study, participants were randomized using a 1:1:1:1 ratio to receive 1 of 4 dose regimens after providing consent and confirmation of eligibility on the study inclusion and exclusion criteria. Upon completion of the interim PK analysis, participants in the second part will be randomized using a 2:1 ratio to receive the treatment regimen or the SoC comparator. The randomization will use a stratified block scheme. Stratification will be by age (6-11 vs 12- less than 18 years of age) and BMI age and sex percentile at entrance (overweight = greater than or equal to 85th% to less than 95th% BMI, obese = greater than or equal to 95th% BMI for age and sex, and obese = greater than or equal to 99th% BMI for age and sex).

#### Masking

Masking is not planned for this study.

### 6.4 STUDY INTERVENTION COMPLIANCE

Research assistants will call, email, or text families at least biweekly (every 2 weeks) to provide encouragement regarding adherence to taking the study supplement. The first dose will be witnessed by study staff at Visit 2. Several methods will be employed to optimize intervention compliance and document compliance. Participants will not initiate treatment unless they demonstrate daily diary card adherence during the run-in. This will minimize dropouts due to non-adherence. At Visit 1, participants will be given diary cards (without a line to record Vitamin D dosing) and taught to use them to document asthma medication use and asthma symptoms. At visits 2 -5, diary cards for dosing visits will be given to the participant to use to document adherence to daily Vitamin D dosing as well as to document asthma medication use and asthma symptoms. Pharmacists/designees will perform pill count from sealed bottles prior to dispensing to subjects as outlined in the Drug Accountability memo (March 4, 2020) to pharmacists from the ISPCTN DCOC.

At visits 6-8, participants will again be given daily dairy cards (without the line to record Vitamin D dosing) to document asthma medication use and asthma symptoms. Similar diary cards have been used successfully in numerous large asthma studies to bolster adherence to study drug.(80, 81)

During monthly clinic visits for which Vitamin D was given (at the previous visit), sites are to measure participant dosing compliance by pill counts and by participant diary review, identifying non-compliance (taking less than 75% of vitamin D3). Study staff will be trained to review the diary cards at the visit with the participant to clarify any issues or questions, and to provide positive feedback to participants who demonstrate good adherence and ongoing encouragement when warranted at each visit. Sites are to make every effort to schedule participant clinic visits  $\pm 7$  days of the scheduled visit, per the schedule of activities. Enrolling ISPCTN study sites will receive a minimum of 1 on-site monitoring visit by a member of the DCOC or their designee, as described in the Clinical Monitoring Plan. During the monitoring visit, drug accountability will be performed. Sites are to maintain all shipment records and non-dispensed product received from Bio-Tech Pharmacal, Inc.

## 6.5 CONCOMITANT THERAPY

All drugs and/or treatments, other than specific excluded medications, are permitted while on study drug. Use of an undisclosed excluded medication will be a protocol deviation. Similarly, if a participant uses an excluded medication and the instructions in this section are not followed, the use of the excluded medication will be a study deviation. Several medications can interfere with the absorption or metabolism of vitamin D and alter 25(OH)D levels. If a participant must start on an excluded medication during the trial period (i.e. after study drug starts), the participant will discontinue study drug but will continue with all other study procedures. New medications prescribed for the control of asthma (including systemic corticosteroids used for brief time periods [less than 14 days] or change in asthma controllers) will not result in withdrawal from study drug but will be recorded. Participants will be advised not to take additional supplements containing more than 1000 international units (IU) of vitamin D per day. All concomitant medications including dates of use, formulation, dose, and frequency will be documented during the study period.

If a participant is taking over-the-counter vitamin supplement(s), study personnel will find out what supplement(s) are being taken. This will be done by showing the participants and caregivers pictures of supplements that are commonly used by the general public. If the supplement is not in the picture set, then the caregiver will be asked to bring in the bottle at the next visit. The caregiver will also be asked how frequently the supplement is taken. Once the supplement is identified, the study team can verify the dose of vitamin D that is being taken by the participant. Children will be allowed to participate if, at the initial visit, the daily dose of vitamin D is less than or equal to 1,000 IU per day.

Concomitant medications will be verified at every visit; the study team will, therefore, be able to provide on-going guidance and counseling regarding participants' daily intake of vitamin D from over-the-counter vitamins. If a study participant changes over-the-counter vitamins and the vitamin D dose changes to greater than 1,000 IU per day, the study team will ask the participant/caregiver to reduce the over-the-counter vitamin D dose to 1,000 IU per day or less. If the participant/caregiver does not follow the request

and the participant's vitamin D dose remains greater than 1,000 IU per day, the participant will be removed from the study.

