### **Concomitant Medications**

Notes: changes in the medications below while on study could alter PK of vitamin D and information regarding such changes must be captured. Participants would not necessarily have to be withdrawn from the study, but changes in dose for any drug in the following list must be documented.

- Anti-epileptic drugs
- Digoxin, calcium channel blockers
- Statins
- Calcium supplements

---

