If a participant develops elevated serum calcium greater than or equal to  $1.5 \times \text{ULN}$  or 25(OH)D level greater than 100 ng/ml by local lab, the participant will remain off study drug through the duration of the study, but will continue with all other study procedures. See Section 8.2 for further safety assessment information.

2. Any documented adverse event, which in the opinion of the site investigator warrants halting of study drug for participant safety.

If a participant develops elevated serum calcium greater than or equal to  $1.5 \times \text{ULN}$  or 25(OH)D level greater than 100 ng/ml, the participant will remain off study drug through the duration of the study, but will continue with all other study procedures.

The data to be collected at the time of study intervention discontinuation will include the following:

- Reason for discontinuation
- Serum 25(OH)D and serum calcium
- Urine calcium/creatinine ratio
- Concomitant medications (including vitamin D3 daily dose at screening in either individual supplement or as a part of a multivitamin)

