## 7.2 PARTICIPANT DISCONTINUATION/WITHDRAWAL FROM THE STUDY

An investigator may discontinue or withdraw a participant from the study for the following reasons:

- Participant request. Participants are free to withdraw from participation in the study at any time for any reason.
- New medical issues that would make continuing in the study dangerous for the participant
- Pregnancy
- Significant study intervention non-compliance at the discretion of the site investigator
- At the discretion of the investigator

The reason for participant discontinuation or withdrawal from the study will be recorded. Participants who sign the informed consent form (i.e., are enrolled) but do not receive the study intervention may be replaced. Participants who sign the informed consent form, receive the study intervention, and subsequently withdraw or are withdrawn or discontinued from the study will not be replaced.

Participants who are withdrawn or who discontinue from the study for any reason are encouraged to return for final study procedures.

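### Section 6.5 automatically removes a child from the study for continued over-the-counter vitamin D above 1,000 IU/day, where the plan's other mandatory post-randomisation rules stop study drug and keep follow-up

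*Combined protocol and SAP*

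**What the plan says.** Section 6.5 allows over-the-counter vitamin D up to 1,000 IU/day. If a child moves above that, the site asks the family to reduce it. If they do not and "the participant's vitamin D dose remains greater than 1,000 IU per day, the participant will be removed from the study". The wording leaves the investigator no choice.

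The same section treats a child who has to start an excluded medication differently: "the participant will discontinue study drug but will continue with all other study procedures". Section 7.1 does the same for high serum calcium or a 25(OH)D above 100 ng/ml: "the participant will remain off study drug through the duration of the study, but will continue with all other study procedures". Section 8.2 repeats that arrangement, and Section 7.1 opens by separating stopping the supplement from leaving the study. For other drugs that could alter vitamin D kinetics, the note in Section 6.5 says "Participants would not necessarily have to be withdrawn from the study"; changes are documented.

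Study-level withdrawal is covered in Section 7.2, where it is discretionary: "An investigator may discontinue or withdraw a participant from the study for the following reasons". The closest behavioural parallel on that list is "Significant study intervention non-compliance at the discretion of the site investigator".

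On data capture, Section 6.5 says "Concomitant medications will be verified at every visit" and "All concomitant medications including dates of use, formulation, dose, and frequency will be documented during the study period".

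**The concern.** The rule ends scheduled observation of a child who is taking extra, uncontrolled vitamin D on top of a study dose that may be 8,000 IU/day in Part 2. A child whose 25(OH)D has already passed 100 ng/ml is kept and followed. On safety grounds that ordering is hard to justify.

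Three things are at stake:

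- the serial urine calcium/creatinine checks;
- the local Week 28 level, which under Section 8.2 triggers a recheck four weeks later if it exceeds 80 ng/ml;
- an observed Week 16 value.

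Removal does not keep the extra intake out of the PK data either. The intake comes to light only after it has begun, and under Section 9.3 one PK sample is enough for a child to enter the population PK analysis. Samples already taken during the extra intake therefore stay in.

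**Working it through.** **1. Compare every rule that acts after randomisation.**

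| Trigger | Section | Study drug | Remaining procedures |
|---|---|---|---|
| Excluded medication has to be started | 6.5 | Stopped | Continue |
| Serum calcium at or above 1.5 × ULN, or 25(OH)D above 100 ng/ml | 7.1, 8.2 | Stopped | Continue |
| Pregnancy | 8.3.9, 7.2 | Stopped | Withdrawal discretionary |
| Study-drug non-compliance | 7.2 | Investigator decides | Withdrawal discretionary |
| Other drugs that may alter vitamin D kinetics | 6.5 | No automatic stop | Not necessarily withdrawn |
| Over-the-counter vitamin D stays above 1,000 IU/day | 6.5 | Ends with removal | End automatically |

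The only other mandatory removal in the protocol is the run-in diary rule at Visit 2 (Section 8.1.1.1), which acts before randomisation. The over-the-counter rule therefore stands alone.

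**2. Count what a removed child may lose.** Section 8.1.2 requires central 25(OH)D at Visits 2 to 9, which is 8 samples without the optional draw. Urine calcium/creatinine on treatment is due at Visits 3 to 6, which is 4 checks. For removal after a given visit:

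| Removed after | Central samples remaining | Urine checks remaining |
|---|---|---|
| Visit 3 | 9 − 3 = 6 of 8 | 6 − 3 = 3 of 4 |
| Visit 4 | 9 − 4 = 5 of 8 | 6 − 4 = 2 of 4 |
| Visit 5 | 9 − 5 = 4 of 8 | 6 − 5 = 1 of 4 |

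The maximum assumes that the intake is found at Visit 3, the first scheduled medication review after randomisation, and that removal follows before Visit 4. If the site waits until Visit 4 to see whether the family has complied, the Visit 4 row applies. The local Week 28 level may also be lost.

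**3. Size the effect on the Part 2 test.** The plan's requirement of 31 completers (Section 9.2) reproduces. With p0 = 0.50, p1 = 0.75, one-sided 0.05 and power 0.90:

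n = [(1.6449 × √(0.50 × 0.50) + 1.2816 × √(0.75 × 0.25)) / 0.25]² = [(0.8224 + 0.5549) / 0.25]² = 30.35, rounded up to 31.

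Cohort A is 63 × 2/3 = 42. Section 9.5 scores premature withdrawals as non-responders. With all 42 in the denominator, one child removed before Week 16 moves the proportion by at most 1/42 = 2.4 percentage points. That child also uses one of the 42 − 31 = 11 places between those randomised and the completers required. The documents give no expected number of such children.

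**The case against.** The strongest defence is that the rules answer different situations. An excluded medication is a medical need and a high calcium is a laboratory finding. Here a family has been counselled and asked, and still gives the study agent off protocol, which raises the measured analyte. That justifies stopping study drug and distrusting the Week 16 value. It does not justify ending observation, since the plan leaves withdrawal for study-drug non-compliance, which is also behavioural, to the investigator.

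The safeguards that already exist count in the plan's favour:

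- Section 7.1 collects serum 25(OH)D, serum calcium and urine calcium/creatinine when study drug stops.
- Section 7.1 also provides a termination visit, with safety labs and a focused examination, when a child asked to stop drug then leaves the study.
- Section 7.2 encourages withdrawn children to return for final procedures.

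A removed child should therefore usually get an exit check. These provisions do not replace serial checks.

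The IRB's role is a fair caution. The summary of changes from version 01 to 02 records that the IRB asked for information on allowable over-the-counter dosage. It does not record a request for removal.

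Four stronger readings are tempting, and the documents do not support them:

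- **The sections contradict each other.** They do not. This is an inconsistency of principle, since each rule can be followed as written.
- **The Week 28 level is lost in every case.** Section 7.2 may preserve it, because final procedures are not defined and could include it.
- **Children will be removed after dosing ends.** Table 1 and the medication check at every visit make this possible. However, Section 6.5 opens with what is permitted while on study drug, and the follow-up visit list in Section 8.1.1.1 does not name medication review. It remains an inference.
- **The PK model mishandles over-the-counter intake because of this rule.** Up to 1,000 IU/day is allowed for every child, so whether such intake enters as dose input is a separate question.

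**Conclusion.** The concern holds as an optional improvement. Section 6.5 contains the only automatic post-randomisation removal, and it departs from the plan's own principle of stopping drug and keeping follow-up. The loss per child is up to 6 of 8 central samples and up to 3 of 4 on-treatment urine checks, with the Week 28 local level at risk and partial cover from the exit provisions.

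The number of children is not stated. I assume it is low, and it could be zero. A reader might infer a material threat to Part 2 power. The documents do not support that: the shift is at most 2.4 points per child, and the change proposed here leaves scoring before Week 16 as it is. This assumes that removal counts as premature withdrawal under Section 9.5.

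The gain is safety follow-up and an observed Week 16 value. It is not clean washout data, because later samples would be affected if the extra intake continued.

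**What to change.** - **Section 6.5.** Replace the removal clause with: *will discontinue any remaining study drug, have the extra vitamin D dose and dates recorded, and be asked to continue all other study procedures through Week 28.*
- **Section 9.5.** Add that children who meet this rule before Week 16 remain non-responders in the primary Part 2 analysis, and that their observed Week 16 value is used only in a sensitivity analysis. This differs from children kept in the study after stopping drug for other reasons. The difference is justified because extra intake of the same agent would inflate the observed value.
- **Section 9.4.2.** Add one PK sensitivity run that excludes samples taken after the extra intake began.

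The cost is one sentence in each section, with IRB approval before implementation as the Statement of Compliance requires. The IRB should be told why the clause changes, since it asked for the over-the-counter dosage text. No visits are added, and dose and dates are already recorded. The downside is that some later samples will reflect off-protocol intake known only from the family's report.

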### **Excluded medications**

- Oral or IV steroids (including prednisone and equivalent dexamethasone or other steroid dose) greater than 10 mg/day in the 30 days prior to the screening visit or during the run-in period.
  - Oral or parenteral steroids, including doses greater than 10 mg/day, may be used as an acute asthma control medicine during trial period as stated above.
- Vitamin D2 within the 30 days prior to the screening visit or during the run-in period.
- Vitamin D3 supplementation with a daily dosage of greater than 1000 IU in an individual supplement form or as part of a multivitamin within the 30 days prior to the screening visit or during the run-in period.

### **Concomitant Medications**

Notes: changes in the medications below while on study could alter PK of vitamin D and information regarding such changes must be captured. Participants would not necessarily have to be withdrawn from the study, but changes in dose for any drug in the following list must be documented.

- Anti-epileptic drugs
- Digoxin, calcium channel blockers
- Statins
- Calcium supplements

---

#### **6.5.1 RESCUE MEDICINE**

The study team will advise participants to have access to asthma rescue medications (typically albuterol sulfate) for exacerbations of asthma symptoms per standard of care. Management of asthma symptoms will be performed by the participant's routine medical provider. Oral or parenteral steroids are allowed as rescue medicines for asthma exacerbations and should be recorded in the CRF. There is no anticipated need for a rescue medication for the study drug.

## 7 STUDY INTERVENTION DISCONTINUATION AND PARTICIPANT DISCONTINUATION/WITHDRAWAL

### 7.1 DISCONTINUATION OF STUDY INTERVENTION

Discontinuation from taking vitamin D supplements does not mean discontinuation from the study, and remaining study procedures should be completed as indicated by the study protocol. If a clinically significant finding is identified such as an elevated urine calcium/creatinine ratio (greater than 0.37 on 2 measurements), elevated serum calcium level (greater than  $1.5 \times \text{ULN}$ ), or 25(OH)D level greater than 100 ng/ml after enrollment, the investigator or qualified designee will determine if any change in participant management is needed including discontinuation of vitamin D supplements. If a participant is discontinued from study drug (vitamin D supplement), he or she will be asked to complete any remaining study visits in order to assure his or her safety and for the sake of completeness of data collection. If a participant who has been asked to stop taking study drug terminates (for any reason) from the study, site coordinators will make reasonable efforts to complete a termination visit. The termination visit will include routine labs (safety labs at minimum) and a focused physical exam.

Rules for halting of study drug:

1. Spot urine calcium/creatinine ratio greater than 0.37 and subsequent serum calcium above  $1.5 \times \text{ULN}$  for the local laboratory. Because dehydration can artificially inflate the calcium/creatinine ratio, participants will be counseled on consuming adequate fluids throughout the study. Participants who have an elevated spot urine calcium/creatinine ratio will be asked to consume 6 to 8 eight-ounce glasses of water per day, and to return within 2 business days of the site team receiving initial lab results for a repeat calcium/creatinine ratio. If the repeat ratio is less than or equal to 0.37, study medication will be continued without interruption. If the ratio remains greater than 0.37, a local serum calcium level and local 25(OH)D will be checked. If the serum calcium is less than  $1.5 \times \text{ULN}$  and 25(OH)D is less than 100 ng/ml, the participant will continue study drug without interruption.

If a participant develops elevated serum calcium greater than or equal to  $1.5 \times \text{ULN}$  or 25(OH)D level greater than 100 ng/ml by local lab, the participant will remain off study drug through the duration of the study, but will continue with all other study procedures. See Section 8.2 for further safety assessment information.

2. Any documented adverse event, which in the opinion of the site investigator warrants halting of study drug for participant safety.

If a participant develops elevated serum calcium greater than or equal to  $1.5 \times \text{ULN}$  or 25(OH)D level greater than 100 ng/ml, the participant will remain off study drug through the duration of the study, but will continue with all other study procedures.

The data to be collected at the time of study intervention discontinuation will include the following:

- Reason for discontinuation
- Serum 25(OH)D and serum calcium
- Urine calcium/creatinine ratio
- Concomitant medications (including vitamin D3 daily dose at screening in either individual supplement or as a part of a multivitamin)

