To ensure safety in this study, spot urine calcium/creatinine levels will be measured at each visit as a screen for hypercalciuria. The study coordinator will instruct the participant and his or her parent, legal guardian, or caregiver to ensure that the child is well-hydrated prior to the study visit. If the urine calcium/creatinine level is greater than 0.37 on a specimen, the participant will be asked again to ensure good hydration and return within 2 business days for a repeat spot urine calcium/creatinine measurement. If the ratio remains greater than 0.37, then a serum calcium level and 25(OH)D for the local laboratory will be obtained.(75) If serum calcium is greater than  $1.5 \times \text{ULN}$  or the 25(OH)D level is greater than 100 ng/ml, the participant will have supplementation stopped but will be asked to return for remaining study visits in order to obtain data on vitamin D clearance and for safety assessments. Vitamin D supplementation ends at 16 weeks (day  $112 \pm 7$ ) for all participants. They will be followed for another twelve weeks for determination of elimination kinetics and for safety assessments. The half-life of vitamin D is variable but is felt to be approximately 2 months.(88) The 12-week follow-up therefore consists of 1.5 half-lives. A serum 25(OH)D level will be drawn for the local laboratory safety measure at week 28 (visit 9; day  $196 \pm 7$ ). If a participant has a serum 25(OH)D level greater than 80 ng/ml at that time, he/she will be asked to return 4 weeks later for a re-check to ensure that the level is not continuing to rise as vitamin D washes out of adipose tissue. If there are any ongoing concerns, further follow up will be determined by the local investigator in collaboration with the child's primary care team and sub-specialists as necessary.

This is not an asthma treatment study. We will monitor asthma symptoms, however. Each participant is required to have an identified asthma-care provider at entry. This can be a specialist or a primary care provider. If it is found that a participant's asthma is poorly controlled, he or she will be referred back to the primary asthma-care provider for reevaluation and further treatment.

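### Section 7.1 gives two different actions for a 25(OH)D above 100 ng/ml during dosing: investigator judgement in its opening paragraph, mandatory stopping in its halting rules

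*Combined protocol and SAP*

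**What the plan says.** Section 7.1 opens with a general paragraph. Its examples of clinically significant findings are "an elevated urine calcium/creatinine ratio (greater than 0.37 on 2 measurements), elevated serum calcium level" above 1.5 × ULN, and a 25(OH)D above 100 ng/ml after enrollment. For these, "the investigator or qualified designee will determine if any change in participant management is needed including discontinuation of vitamin D supplements".

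A headed set of halting rules follows. Under rule 1, a repeat urine ratio above 0.37 leads to a local serum calcium and a local 25(OH)D. If calcium is below 1.5 × ULN and "25(OH)D is less than 100 ng/ml, the participant will continue study drug without interruption". The text then reads "If a participant develops elevated serum calcium greater than or equal to" 1.5 × ULN, or a "25(OH)D level greater than 100 ng/ml by local lab, the participant will remain off study drug through the duration of the study". After rule 2 the same sentence appears again without naming a laboratory: "25(OH)D level greater than 100 ng/ml, the participant will remain off study drug through the duration of the study".

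Section 8.2 describes the same urine sequence. "If serum calcium is greater than" 1.5 × ULN or "the 25(OH)D level is greater than 100 ng/ml, the participant will have supplementation stopped". Section 8.3.3.3, in a parenthesis within the list of expected adverse events, says the intervention stops once the level gets to 100 ng/ml. Section 8.1.2 lets the local investigator order local 25(OH)D levels for safety at his or her discretion.

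**The concern.** The opening of 7.1 and the rules beneath it name the same analytes at essentially the same limits but attach different actions. One makes discontinuation a matter of judgement; the other makes it automatic for the rest of the study. Neither is made subject to the other.

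This is a multi-center, open-label trial in children, and these are its laboratory-based stopping limits. Given the same result, one site could stop study drug and another could continue it, each relying on 7.1. Stopping also decides who completes 16 weeks of dosing, and so who stays in the per-protocol population described in section 9.5.

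**Working it through.** The check is mainly a comparison of text. The arithmetic at the end only gauges scale.

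**Action statements side by side**

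| Place | 25(OH)D trigger | Calcium trigger | Action |
|---|---|---|---|
| 7.1, opening | above 100 | above 1.5 × ULN | investigator or designee decides |
| 7.1, sentence closing rule 1 | above 100, local laboratory | at or above 1.5 × ULN | off drug for the rest of the study |
| 7.1, sentence after rule 2 | above 100, laboratory not named | at or above 1.5 × ULN | off drug for the rest of the study |
| 8.2 | above 100, after repeat urine ratio above 0.37 | above 1.5 × ULN | supplementation stopped |
| 8.3.3.3 | reaching 100, no condition stated | none | intervention stopped |

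For 25(OH)D there is one discretionary statement against four mandatory ones. For calcium there is one against three.

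**Where the conflict bites**

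- *Inside the urine pathway.* A local value above 100 ng/ml meets both the opening paragraph and the halting rules. Reading the specific rules as controlling is natural here, but it is not stated.
- *Outside the urine pathway.* A discretionary local level under 8.1.2 is not part of the sequence in rule 1 or 8.2. The opening of 7.1 then calls for judgement, while the unqualified sentence after rule 2 keeps the child off drug.
- *In the other direction.* For a urine ratio above 0.37 on two measurements, the opening leaves discontinuation to judgement. Rule 1 continues drug without interruption when calcium and 25(OH)D are below their limits.

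**Secondary wording differences**

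- At exactly 100 ng/ml, 7.1 gives no action (continue if less, stop if greater), while 8.3.3.3 stops.
- At exactly 1.5 × ULN calcium, both closing sentences in 7.1 stop drug. The opening line of rule 1 and section 8.2 do not trigger. Rule 1's continue clause requires calcium below the limit, so no passage says to continue at that value.
- 8.3.3.3 states the stop without condition. The only local 25(OH)D required during dosing follows a repeat urine ratio above 0.37 (Schedule of Activities footnote g; 7.1; 8.2).

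**Illustrative size: how many children might exceed 100 ng/ml**

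Inputs: adult Week 21 increments in section 4.3 of 27.8 (SD 10.2) ng/ml at 5,000 IU/day and 48.1 (SD 19.6) at 10,000 IU/day; baseline about 20 ng/ml (4.3), with 10 to 29.9 as the eligibility range (5.1); normality assumed.

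Formula: z = (100 − baseline − mean increment) / SD.

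- 5,000 IU/day, baseline 20: z = 52.2/10.2 = 5.12, probability 1.5 × 10⁻⁷.
- 10,000 IU/day, baseline 20: z = 31.9/19.6 = 1.63, probability 5.2%.
- 10,000 IU/day, baseline 10: z = 41.9/19.6 = 2.14, probability 1.6%.
- 10,000 IU/day, baseline 29.9: z = 22.0/19.6 = 1.12, probability 13.1%.

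Cohort A averages (50,000 + 111 × 8,000)/112 = 8,375 IU/day, or 8,446 with 112 daily doses, so it lies between the two adult doses. I do not interpolate, because 4.3 describes the response as not linear. Expected Cohort A size is 2/3 × 63 = 42. At baseline 20 the bracket is 0 to 42 × 0.052 = 2.2 children. The upper end is 0.7 at baseline 10 and 5.5 at baseline 29.9.

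**Illustrative size: Week 16 level after an early stop**

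Take a child at 100 ng/ml who is stopped at Week 4, the first scheduled urine test during dosing, and decays toward baseline B: level = B + (100 − B) × 2^(−weeks/half-life). The half-life is 8 weeks (8.2 equates 12 weeks with 1.5 half-lives) or 13 weeks (the 3-month end of the range in 2.2).

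| Time off drug | Half-life | B = 10 | B = 20 | B = 29.9 |
|---|---|---|---|---|
| 12 weeks (nominal) | 8 weeks | 41.8 | 48.3 | 54.7 |
| 12 weeks (nominal) | 13 weeks | 57.5 | 62.2 | 66.9 |
| 14 weeks (Day 21 to Day 119) | 8 weeks | 36.8 | 43.8 | 50.7 |
| 14 weeks (Day 21 to Day 119) | 13 weeks | 52.7 | 57.9 | 63.1 |

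Only the combination of extreme visit windows, lowest baseline and shorter half-life falls below 40 ng/ml. At nominal visit days the half-life would have to be under 7.6 weeks (B = 10) or 6.0 weeks (B = 20). A later stop leaves less time to decline.

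**The case against.** The best defence is that the opening of 7.1 is a general introduction and the headed rules are specific, so the rules control. Almost every other statement says stop, and a site continuing drug above 100 ng/ml would be relying on one introductory sentence. The Schedule of Activities plans no local 25(OH)D during dosing except through the urine pathway. The version 04 to 05 change log describes the halting tests as local and following a repeat urine ratio, which suggests that the unqualified sentence after rule 2 is an unedited duplicate. Section 8.3.3.3 is a parenthesis, not an operating rule.

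Part of this stands. Inside the urine pathway most readers would follow the numbered rules, and the laboratory and boundary points are secondary. But the opening names the same analytes and expressly includes discontinuation in what is left to judgement, with nothing making it subject to the rules below. Discretionary levels under 8.1.2 remain outside the pathway. A change log may show intent but does not alter the current text.

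It is also fair to say that the figures count levels above 100 ng/ml, not children who would meet conflicting instructions. They rest on adult data, and the decay model is simple: 8.2 itself allows for levels still rising as vitamin D leaves adipose tissue. The contradiction stands without them.

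**Conclusion.** The concern holds. The sections prescribe different actions for a 25(OH)D above 100 ng/ml and for a calcium above 1.5 × ULN, and give no order of precedence. Confidence in this is high because it rests on the current text alone.

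The number of children involved is probably small, and a stop would rarely change the Week 16 response. Those statements of size depend on adult increments, normality, assumed half-lives and simple exponential decline. The weight of the point is consistent safety handling of children across sites, which justifies a correction even though the Part 2 test is unlikely to be affected.

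**What to change.** The sponsor should reconcile section 7.1 (opening paragraph and halting rules), section 8.2 and section 8.3.3.3 into one statement that settles:

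1. whether the action is mandatory or at investigator judgement, and whether the numbered rules control over the opening paragraph;
2. which laboratory result counts, including a discretionary local level taken outside the urine pathway;
3. what happens at exactly 100 ng/ml and at exactly 1.5 × ULN calcium.

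The other sections should then repeat or point to that statement. Which rule or limit is right is a clinical decision for the sponsor. The cost is protocol wording only, with no new test, sample or visit.
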